8.2.5.2 ECOG Performance Status

Eastern Cooperative Oncology Group performance status will be assessed at the timepoints specified in the SoA of the relevant individual modules based on the following:

0	Fully active; able to carry out all usual activities without restrictions
1	Restricted in strenuous activity, but ambulatory and able to carry out light work or work of a sedentary nature (eg, light housework or office work)
2	Ambulatory and capable of self-care, but unable to carry out any work activities; up and about more than 50% of waking hours
3	Capable of only limited self-care; confined to bed or chair more than 50% of waking hours
4	Completely disabled; unable to carry out any self-care and totally confined to bed or chair
5	Dead

Any significant change from baseline or screening must be reported as an AE, as described in Section [8.3.5](#).

8.3 Adverse Events and Serious Adverse Events

The Investigator is responsible for ensuring that all staff involved in the study are familiar with the content of this section.

The definitions of an AE or SAE can be found in [Appendix B](#).

Adverse events will be reported to the Investigator by the patient (or, when appropriate, by a caregiver, surrogate, or the patient's legally authorised representative). The Investigator and any designees are responsible for detecting, documenting, and recording events that meet the definition of an AE.

8.3.1 Time Period and Frequency for Collecting AE and SAE Information

Adverse events and SAEs will be collected from the time of signature of the ICF throughout the treatment period and including the follow-up period (28 days after the last dose of the study intervention). If an event that starts after the defined safety follow-up period noted above is considered to be due to late-onset toxicity to study intervention, it should be reported as an AE or SAE as applicable.

All SAEs will be recorded and reported to AstraZeneca or its designee within 24 hours. The Investigator will submit any updated SAE data to AstraZeneca within 24 hours of it being available.

The method of recording, evaluating, and assessing causality of AEs and SAEs and the procedures for completing and transmitting SAE reports are provided in [Appendix B](#).

If the Investigator becomes aware of an SAE with a suspected causal relationship to study intervention that occurs after the end of the clinical study in a patient treated by him/her, the Investigator shall, without undue delay, report the SAE to the Sponsor.

8.3.2 Follow-up of AEs and SAEs

After the initial AE/SAE report, the Investigator is required to proactively follow each patient at subsequent visits/contacts. All SAEs and non-SAEs will be followed until resolution, stabilisation, the event is otherwise explained, or the patient is lost to follow-up.

Any AEs that are unresolved at the patient's last AE assessment or other assessment/visit as appropriate in the study are followed up by the Investigator for as long as medically indicated (this may be beyond the 28 days after the last dose of study intervention), but without further recording in the eCRF. AstraZeneca retains the right to request additional information for any patient with ongoing AE(s)/SAE(s) at the end of the study, if judged necessary.

Adverse Event Variables

The following variables will be collected for each AE:

- AE (verbatim)
- The date when the AE started and stopped
- CTCAE grade/changes in CTCAE grade
- Whether the AE is serious or not
- Investigator causality rating against the investigational product(s) (yes or no)
- Action taken with regard to investigational product
- Outcome

In addition, the following variables will be collected for SAEs:

- Date AE met criteria for SAE
- Date Investigator became aware of SAE
- AE is serious due to
- Date of hospitalisation
- Date of discharge
- Causality assessment in relation to study procedure(s)
- Causality assessment to other medication
- Description of the SAE
- Probable cause of death

- Date of death
- Autopsy performed

The grading scales found in the revised NCI CTCAE v5.0 will be utilised for all events with an assigned CTCAE grading. For those events without assigned CTCAE grades, the recommendation in the CTCAE criteria that converts mild, moderate, and severe events into CTCAE grades should be used. A copy of the CTCAE v5.0 can be downloaded from the CTEP website (<http://ctep.cancer.gov>).

8.3.3 Causality Collection

The Investigator should assess causal relationship between each study intervention (AZD0466 and combination treatment) and each AE, and answer ‘yes’ or ‘no’ to the question ‘Do you consider that there is a reasonable possibility that the event may have been caused by the study intervention?’

For SAEs, causal relationship should also be assessed for other medication and study procedures. Note that for SAEs that could be associated with any study procedure the causal relationship is implied as ‘yes’.

A guide to the interpretation of the causality question is found in [Appendix B](#) to CSP.

8.3.4 Adverse Events Based on Signs and Symptoms

All AEs spontaneously reported by the patient or reported in response to the open question from the study site staff: ‘Have you had any health problems since the previous visit/you were last asked?’, or revealed by observation will be collected and recorded in the eCRF. When collecting AEs, the recording of diagnoses is preferred (when possible) to recording a list of signs and symptoms. However, if a diagnosis is known and there are other signs or symptoms that are not generally part of the diagnosis, the diagnosis and each sign or symptom will be recorded separately.

8.3.5 Adverse Events Based on Examinations and Tests

The results from the CSP mandated laboratory tests, vital signs, and ECGs will be summarised in the CSR.

Deterioration as compared to baseline in protocol-mandated laboratory values or vital signs should therefore only be reported as AEs if they fulfil any of the SAE criteria, DLT criteria, are the reason for discontinuation of study intervention, or are considered to be clinically relevant as judged by the Investigator (which may include but is not limited to consideration as to whether treatment or non-planned visits were required or other action was taken with the study intervention, eg, dose adjustment or dose interruption).

If deterioration in a laboratory value/vital sign is associated with clinical signs and symptoms, the sign or symptom will be reported as an AE and the associated laboratory result/vital sign will be considered as additional information. Wherever possible the reporting Investigator uses the clinical, rather than the laboratory term (eg, anaemia versus low haemoglobin value). In the absence of clinical signs or symptoms, clinically relevant deteriorations in non-mandated parameters should be reported as AE(s).

Deterioration of a laboratory value, which is unequivocally due to disease progression, should not be reported as an AE/SAE.

Any new or aggravated clinically relevant abnormal medical finding at a physical examination as compared with the baseline assessment will be reported as an AE unless unequivocally related to the disease under study.

8.3.6 Adverse Events of Special Interest

An AESI is an AE, serious or non-serious, that is of scientific and medical interest specific to the understanding of the study intervention and may require closer monitoring, with collecting of additional information by the Investigator and reporting these to the Sponsor. The rapid reporting of AESIs by the Investigator allows ongoing surveillance of these events in order to further characterise and understand them in relation to the use of the study intervention. All AESIs should be recorded in the eCRF as soon as possible, preferably within 24 hours. All AESIs that are also serious (ie, are SAEs) should be reported to AstraZeneca Patient Safety within 24 hours, as per safety reporting requirements.

In this study, the following are considered to be AESIs:

- Tumour lysis syndrome ([Appendix G](#))
- Hepatotoxicity, including potential Hy's Law, DILI, and bilirubin increase with transaminase (ALT or AST or both ALT and AST) increase
- QRS amplitude decrease

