4.5 Criteria for Stopping or Pausing the Study Recruitment

AstraZeneca reserves the right to pause recruitment, temporarily suspend or permanently terminate this study or components of the study at any time. AstraZeneca may at any point during the study, pause enrolment if at least one of the following occurs:

- Fatal event deemed related to study intervention by the Sponsor and in discussion with the SRC (probable or certain causality based on World Health Organization-The Uppsala Monitoring Centre [WHO-UMC] after full etiological work-up). This will also result in a comprehensive review of safety.
- Unexpected and life-threatening events deemed related to study intervention by the Sponsor and in discussion with the SRC. Note: As thrombocytopenia is an on-target effect it will be further addressed at the time of the SRC (Part A) or the safety interim analysis (Part B) and will not be considered as stopping criteria.

- Sponsor decision that study patients are placed at undue safety risk (also covered in Section 4.4)
- Sponsor decision to discontinue the development of the study intervention in the proposed indications.

During Part A of Module 1, AZD0466 monotherapy dose escalation, AstraZeneca pharmacovigilance process and the SRC will evaluate toxicities study-wide (including evaluation of previous doses). During Part B of Module 1, AZD0466 monotherapy dose expansion, a safety analysis will be performed at the time of the first interim analysis in each cohort (Cohort B1 at [redacted] patients, Cohort B2 at [redacted] patients and Cohort B3 at [redacted] patients), pooling safety data from all available patients. The study recruitment may be paused, pending investigation by the Sponsor and in discussion with SRC, if > [redacted] % of patients experience safety events that meet the DLT criteria, see Section 10.6.6.3 (including AEs of special interest [Section 8.3.6]), the SRC, will decide to stop the study, modify the study, or continue the study, based on the overall risk benefit of the agent. Throughout the expansions, the AZ safety team and the SRC, will regularly review cumulative safety data including, but not limited to, toxicities that meet the DLT criteria.

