8.2.3 Electrocardiograms

Digital 12-lead ECGs (triplicate ECGs, all 3 within a 5-minute time period) will be obtained after the patient has been resting in a supine position for at least 10 minutes. A single safety ECG will be collected if a Holter continuous ECG (for PK purpose) is being collected simultaneously. If a clinically significant abnormality is noted, triplicate safety ECGs are advised to be collected.

Safety ECGs will be performed at timepoints specified in the SoA of the relevant individual module. Safety ECGs will be measured before vital signs and prior to PK blood draws at matched PK sample timepoints. If an unscheduled ECG is done at any time, then an electrolyte panel (Section 8.2.4) must be collected to coincide with ECG testing.

A standardised ECG machine provided by the central ECG vendor should be used and the patient should be examined using the same machine throughout the study, where feasible. In case the centrally provided ECG machine is unavailable or technical issues occur that preclude

correct measurement, local ECGs (using the site owned device) may be performed instead. Standard ECG parameters to be determined will include HR/RR, PR, QRS, QT, and QTcF (QT interval corrected for HR using Fridericia's formula) intervals.

After the ECGs have been recorded, the Investigator or designated physician will review each of the ECGs at all timepoints for the presence of abnormalities (including rhythm, ECG intervals, or repolarisation abnormalities) and may refer to a local cardiologist if appropriate. A paper copy of the ECG should be filed in the patient's medical records. For all ECGs, an overall evaluation and interpretation should be recorded by the Investigator or designated physician. Any clinically significant abnormalities detected require a confirmatory ECG.

Refer to Section [6.6.6.5](#) for management of cardiac findings and cardiovascular parameters that require treatment to be withheld or increased monitoring.

Situations in which ECG results should be reported as AEs are described in Section [8.3.5](#).

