ECG = electrocardiogram; PK = pharmacokinetics; SRC = Safety Review Committee.

Continuous 12-lead ECG Recordings (Holter)

Patients enrolled in cohorts for which the treatment dose has not been cleared by the SRC in previous AZD0466 clinical studies will require continuous recordings of 12-lead ECGs (12-lead Holter devices) for the purpose of PK modelling. When electrocardiogram Holter monitoring is performed, extractions will capture PR, QRS, QT, QTcF, and RR intervals. Recording should be performed as specified in [Table 13](#) of the SoA and [Table 16](#) above, with recording commencing on C1D8 pre-infusion to cover the 24-hour timepoint (prior to PK sampling). The timing of ECGs may be altered depending on the emerging PK profile. The standardised 12-lead Holter device will be provided by the central ECG vendor who will provide the central ECG reads.

The 12-lead Holter devices will always be fitted and safely removed by the Investigator or a trained designee.

The schedule of continuous ECG recordings may be increased, reduced, or stopped at any time during the study, if supported by emerging data and with the agreement of the SRC.

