- Hepatotoxicity, including potential Hy's Law, Drug-induced liver injury, Bilirubin increases with transaminase (ALT or AST, or both ALT and AST) increase
- QRS amplitude shortening

Other categories may be added, or existing terms may be modified as necessary. An AstraZeneca medically qualified expert after consultation with the Global Patient Safety Physician has reviewed the AEs of interest and identified which higher-level terms and which preferred terms contribute to each AESI. Further reviews may take place prior to database lock (DBL) to ensure any further terms not already included are captured within the categories.

Other significant adverse events (OAE)

During the evaluation of the AE data, an AstraZeneca medically qualified expert reviews the list of AEs that were not reported as SAEs and AEs leading to discontinuation of study treatment. Based on the expert's judgement, AE of particular clinical importance may, after consultation with the Global Safety Physician, be considered other significant adverse events (OAEs) and reported as such in the Clinical Study Report. A similar review of laboratory values, vital signs, ECGs, and other safety assessments will be performed for identification of other significant adverse events. This review takes place prior to database lock, and any AEs identified will be fully documented in meeting minutes. Further review following database lock may result in ad-hoc OAEs being identified, in this case, the other OAEs and resulting summaries will be fully documented in the CSR.

Examples of these are marked haematological and other laboratory abnormalities, and certain events that lead to treatment (other than those already classified as serious), dose reduction or significant additional treatment.

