5.6.9 Electrocardiogram

5.6.9.1 Definitions and Derivations

Electrocardiogram (ECG) parameters (triplicate recordings) will be assessed at baseline as well as throughout the study. The average of the triplicate measures taken will be used in all calculations. ECG parameters include PR, RR, QRS, QT, QTcB, and QTcF. The QTcF is considered as the primary correction method to assess patient cardiac safety.

From these resting 12-lead ECGs values of the QT and RR intervals and the QT interval corrected for heart rate using Fridericia's correction (QTcF) will be derived using the following formula:

$$\text{QTcF} = \frac{\text{QT}}{\sqrt[3]{\text{RR}}} \text{ where RR is in seconds}$$

The values of QTcF (milliseconds) will be re-derived from the values of RR and QT during the creation of the reporting database.

The notable ECG interval values while on treatment are:

- Maximum QTcF, QTcB and QTc intervals > 450 milliseconds, > 480 milliseconds, and > 500 milliseconds.
- Maximum changes from baseline in QTcF and QTcB > 30, >60, and > 90 milliseconds.

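### QRS amplitude decrease is an AESI, but amplitude is not a specified, quantified or tabulated ECG parameter, and the SAP gives the event a different name

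*Protocol*

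**What the plan says.** Protocol 8.3.6 lists three AESIs: tumour lysis syndrome, hepatotoxicity and "QRS amplitude decrease". Table 1 of the protocol places QRS changes and myocardial oedema under cardiovascular toxicity, among the important potential risks. SAP 5.6.2.1 repeats the AESI list but words the third item as "QRS amplitude shortening".

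Three places list ECG variables:

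- Protocol 8.2.3, safety ECGs: "Standard ECG parameters to be determined will include HR/RR, PR, QRS, QT, and QTcF", with the list described as intervals.
- Protocol 10.8.2.3, Holter: "extractions will capture PR, QRS, QT, QTcF, and RR intervals".
- SAP 5.6.9.1: "ECG parameters include PR, RR, QRS, QT, QTcB, and QTcF". The notable values that follow are QTc categories only.

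Amplitude is mentioned as a finding in protocol 8.2.5.1 and SAP 5.6.10.1. In both, a significant QRS amplitude change is an example of what prompts further cardiac imaging. Neither defines significant.

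Protocol 4.5 allows recruitment to be paused in Part B if more than a redacted percentage of "patients experience safety events that meet the DLT criteria, see Section 10.6.6.3 (including AEs of special interest [Section 8.3.6". SAP 11.1.9.1 repeats the rule.

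**The concern.** The AESI is a fall in voltage. In a list of intervals, QRS means duration, and duration can stay normal while amplitude falls. The planned ECG summaries could therefore look unremarkable in a patient who has the event.

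What is at stake is how far the AESI count can be trusted. The event corresponds to a risk that the sponsor ranks as important and was identified from nonclinical data. If detection depends on who reads the tracing, the count mixes the drug's effect with differences between readers and sites. A small number could mean that the effect is rare or that it is seldom noticed, and the planned outputs would not separate the two.

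**Working it through.** There is no stated figure to reproduce. The check sets the relevant sections side by side.

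**1. Is amplitude a listed variable?**

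| Place | Variables | Amplitude? |
|---|---|---|
| Protocol 8.2.3 | HR/RR, PR, QRS, QT, QTcF | No |
| Protocol 10.8.2.3 (Holter) | PR, QRS, QT, QTcF, RR | No |
| SAP 5.6.9.1 | PR, RR, QRS, QT, QTcB, QTcF | No |
| SAP 5.6.9.1, notable values | QTc level and QTc change | No |

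All three parameter lists omit it, and so does the set of notable values.

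**2. Is there an operational definition elsewhere?** No section gives leads, a baseline comparison, a size of fall or a confirmation rule. The other two AESIs differ. Tumour lysis syndrome has criteria and grading in protocol Appendix G and a listing and key-patient table in SAP 5.6.8.2. Hepatotoxicity has Hy's Law thresholds in protocol Appendix E and categories in SAP Table 4. QRS amplitude is the only AESI with neither a definition nor an output based on measurements.

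**3. How would an event reach the AESI table?**

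- The investigator must "review each of the ECGs at all timepoints for the presence of abnormalities (including rhythm, ECG intervals, or repolarisation abnormalities". Amplitude is not among the examples.
- Protocol 8.2.3 refers to 8.3.5 for when an ECG result becomes an AE. The main reporting criteria in 8.3.5 are written for laboratory values and vital signs and do not name ECGs. A further sentence asks for clinically relevant deterioration in parameters that are not mandated to be reported. That leaves a route open, but relevance is left to judgement.
- SAP 5.6.2.2 builds the AESI summaries from preferred-term groupings of reported AEs, not from ECG data.

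The chain is therefore: a reader notices the change, judges it relevant and reports it, and the term is then grouped. If a share *s* of true events passes through this chain, the reported rate is *s* times the true rate. Nothing in the plan lets *s* be estimated.

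**4. How many recordings are involved?** From protocol Table 16:

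- Cycle 1 safety ECGs: Day 1 (2) + Day 2 (1) + Day 4 (2) + Day 5 (1) + Day 8 (2) + Day 9 (1) + Day 15 (2) + Day 22 (2) = 13 timepoints.
- Cycle 2: Day 1 (2) + Day 8 (2) = 4 timepoints.
- From Cycle 4: 2 timepoints in each even cycle.
- Holter extractions: Day 8 (6) + Day 9 (1) = 7 timepoints, only in cohorts at doses that the SRC had not cleared in previous AZD0466 studies.

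None has a specified amplitude output. These counts show how much existing material could be used; they do not measure lost events.

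**5. Does the event feed the pause rule?** The sentence in 4.5 can be read in two ways: AESIs count in their own right, or they count only if they also meet the DLT criteria. Protocol 10.6.6.3 does not name QRS amplitude. It covers cardiac findings of Grade 2 or higher that the investigator considers clinically significant. Under the second reading the link is weaker. Steps 1 to 3 do not depend on which reading is meant.

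**The case against.** A reader might infer that the event is never measured and cannot be detected. The documents do not support that. The ECGs are digital, 12-lead and centrally read (10.8.2.3). The investigator reviews every tracing and records an overall interpretation (8.2.3). Protocol 8.2.5.1 and SAP 5.6.10.1 clearly expect amplitude changes to be seen. The list in 8.2.3 is not worded as exhaustive, and the eCRF and the specifications for tables, figures and listings are separate documents that were not available.

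It is also fair to say that an AESI is a category of adverse event rather than an ECG endpoint, so a count can be produced from preferred terms without a numerical amplitude. The underlying cardiac risk is watched in other ways: scheduled MUGA, MRI or ECHO (screening, Cycle 2 Day 8, Day 8 of every third cycle from Cycle 5, end of treatment), troponin and BNP, and the cardiac rules in 6.6.6.5. Imaging does not depend only on someone noticing a voltage change.

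A reader might further infer that each such event counts towards the pause percentage. The text leaves that open, and a pause is discretionary in any case, following sponsor investigation and SRC discussion.

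These points limit the concern to quality of ascertainment. They do not remove it. Expecting a finding to be noticed is not a rule for when it counts, and imaging and biomarkers measure other things. The difference between the protocol and SAP terms is unaffected.

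**Conclusion.** The point holds as a gap in specification. QRS amplitude decrease is an AESI and a prompt for imaging, but amplitude is not specified, quantified or tabulated in protocol 8.2.3, protocol 10.8.2.3 or SAP 5.6.9.1, and the SAP term does not match the protocol term. Ascertainment rests on investigator reading without a stated criterion, followed by AE coding. A low AESI count would therefore be weak evidence that the effect is absent.

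The size cannot be given as a number of missed events, because the documents contain nothing from which to estimate how often a voltage fall would be noticed. What can be said is that 3 of 3 parameter lists omit amplitude, no section gives a quantitative criterion, and 13 + 4 = 17 scheduled safety ECG timepoints in the first two cycles have no specified amplitude output.

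This rests on two assumptions: that QRS in these lists means duration, which the word intervals in the two protocol lists supports, and that the unseen eCRF, output specifications and vendor data specification do not already include amplitude. The change should be made because it improves the measurement of a named cardiac risk at little cost. The plan's overall cardiac monitoring is not in question here.

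**What to change.** 1. Add QRS amplitude to the variables taken from the central read of the existing digital 12-lead ECGs (protocol 8.2.3 and 10.8.2.3) and to SAP 5.6.9.1. State the leads and the baseline comparison.
2. In SAP 5.6.9.2, summarise absolute and percentage change from baseline by visit. Add a notable-value category whose threshold the sponsor sets; the documents offer none.
3. Replace the SAP term in 5.6.2.1 with the protocol term, "QRS amplitude decrease", before the preferred-term grouping is fixed.
4. State in protocol 4.5 and SAP 11.1.9.1 whether AESIs count on their own or only when they meet the DLT criteria, so that the two documents give one reading.

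The cost is one added field in the central vendor's data transfer and one extra SAP table, with no new visits or recordings. Two things need confirming. The documents do not say that the vendor can export amplitude. Protocol 8.2.3 also allows site-owned machines as a backup, so some ECGs may lack a central amplitude value and should be shown as missing in the table.
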